1.3 Design and methodology

1.3.1 Research design and General Methodological Approach

This study will be designed as a randomized, controlled trial to compare pain and anxiety levels before, during, and after in-clinic abortion in patients with and without a support person in the abortion procedure room. Each procedure day will be randomized into "support person day" ("intervention group") or "non-support person day" ("control group"). This randomization process was chosen as the most effective way to randomize without compromising patient care and study validity. Limitations to the physical space of the health center prevent patient randomization because there is no way to avoid patients knowing which arm of the study they are in: the intervention arm or the control arm.

Randomization will occur at the beginning of each procedure day by a research assistant who will pull from an opaque envelope that contains ten slips of paper, five will be marked with 'A' and the other five marked with 'B'. The half marked 'A' will indicate the procedure day will be assigned as an "intervention" day, and the other half marked 'B' will indicate the day will be assigned as a "control" day. After all ten slips of paper are pulled and ten of the procedure days have been randomized, the research assistant will replace the ten slips of paper and begin the same randomization process until the designated number of participants have been enrolled. The research assistant will initiate enrollment of patients in the study after they have consented for the abortion procedure.

All patients who present at PPSWCF's Tampa Health Center for a dilation and curettage (D&C), whether for elective pregnancy termination or management of early pregnancy complications and who are proficient enough in English to consent and understand the study procedures are eligible for participation and enrollment. Support people will be eligible for participation and enrollment if they are 18 years of age or older, are privately selected by the patient to be their support person, and who are proficient enough in English to consent and understand the study procedures. Support people for minors will be privately selected by the patient in conjunction with their parent/guardian consent.

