1.3.4 Criteria for the selection of subjects

This study will investigate perceptions of pain, anxiety, and satisfaction in patients with a support person in the abortion procedure room ("intervention group"). Recruitment will take place at PPSWCF's Tampa Health Center.

Inclusion criteria:

Patients:

- Any patient who presents and consents for dilation and curettage
- Patient participants 17 and younger must have a legal guardian provide consent for participation, and the patient must provide assent
- Ability to provide written informed consent in English and comply with all study procedures Support Persons:
 - Any person 18 years and older who the patient selects to accompany as their support person
- Ability to provide written informed consent in English and comply with all study procedures Health Care Providers:
 - Any health center staff attending to the enrolled patient in both intervention and control arms of the study
 - Ability to provide written informed consent in English and comply with all study procedures

Exclusion criteria:

- Patients without a support person on-site willing to participate
- Patients or support persons that are unable to provide written informed consent in English and comply with all study procedures-

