1.3.6. Subject recruitment

All patients presenting for an in-clinic abortion at the PPSWCF Tampa Health Center will be approached by research staff and asked if they are interested in participating in the study after they have completed the informed consent for the D&C procedure. They will be given an information sheet describing the study as well as inclusion and exclusion criteria, and will then inform research staff if they are interested in participating. If the patient is interested in participating in the study, their chosen support person will be given an information sheet describing the study, inclusion, and exclusion criteria, and will privately inform research staff if they are interested in serving as a support person. If both parties express interest in participating in the study, they will undergo the informed consent process together in a private setting.

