1.3.7 Admission Procedure

Enrollment: See section 1.3.6 for details on recruitment. Enrollment in the study will occur in person.

1.3.8 Procedure:

Eligibility confirmation and consent:

After the potential patient-subject consents to have a D&C abortion procedure and both the patient and support person pass the eligibility screening, the patient and support person will undergo

the process of informed consent together where both subjects will have an opportunity to ask questions. In the cases of minors, a parent/guardian will also be present during this consent process. Both subjects will be reminded that participation is voluntary and that if either one decide not to participate, their decision will not affect the quality of the patient's routine care, however neither will be eligible to participate, as all subjects must enroll in pairs (support person and patient). The research assistant will confirm that participating subjects understand the study and meet the inclusion and exclusion criteria. Informed consent for study participation will be signed before any study-related procedures are performed and a copy of the consent will be offered to the subject. Participation is considered to start when the subject signs the Informed Consent Form.

Study procedures:

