1.3.12 Study Limitations

Potential weaknesses in the internal validity of this study are addressed through the study design of a randomized controlled trial. Through randomization, the two study groups should theoretically have similar subject characteristics. One potential weakness is that blinding cannot occur. Also, patients in the control group may be dissatisfied and more anxious at baseline due to knowing that they may not have their desired support person in the procedure room.

One limitation in this study is the potential variation among different providers during inclinic abortion; however, all providers will follow the same set standards for the in-clinic abortion procedures. This, combined with the fact that there are only a small number of rotating providers should decrease this potential limitation.

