2. ETHICAL CONSIDERATIONS

This protocol will be submitted to the Chesapeake Institutional Review Board. The trial will also be approved by Planned Parenthood of Southwest and Central Florida (PPSWCF) and Planned Parenthood Federation of America's Clinical Research Department.

No effective health care will be withheld from study subjects. In clinical practice, support persons are not often allowed in the procedure room. If a patient states that she would prefer a support person in the room, but does not want to participate then she will not be eligible for the study and will then be able to have a support person in the procedure room only at the discretion of the provider.

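### The day's arm is drawn before recruitment by the role that then enrols, and nothing conceals it until consent, so the arms can enrol different kinds of pairs

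*Protocol*

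**What the plan says.** Section 1.3.1 randomises procedure days, not patients. On timing and role it says "Randomization will occur at the beginning of each procedure day by a research assistant", who takes a slip from an opaque envelope holding five of each kind. It continues: "The research assistant will initiate enrollment of patients in the study after they have consented for the abortion procedure". Under eligibility confirmation and consent (sections 1.3.7 and 1.3.8), the same role appears again: "The research assistant will confirm that participating subjects understand the study and meet the inclusion and exclusion criteria". Section 1.3.6 describes the approach more loosely. It says of all presenting patients that they "will be approached by research staff and asked if they are interested in participating in the study after they have completed the informed consent". The consent meant there is consent to the procedure.

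Entry turns on willingness. Section 1.3.4 excludes "Patients without a support person on-site willing to participate", and section 1.3.8 makes neither member of a pair eligible if the other declines. Section 1.3.8.2 sends the support person into the procedure room in the intervention arm only; in the control arm they complete surveys. Section 2 deals with a patient who wants company but not the study: she is "able to have a support person in the procedure room only at the discretion of the provider".

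On comparability, section 1.3.12 says: "Through randomization, the two study groups should theoretically have similar subject characteristics". It goes on to mention the lack of blinding and possible extra baseline anxiety in control patients. It does not mention that the arms might enrol different people.

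**The concern.** Randomising days balances who attends the clinic. It does not balance who agrees to join once the day's arm is set. If the recruiter or the pair knows the arm, two kinds of selection are open:

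- On a control day, a patient who strongly wants company has some reason to decline, since outside the study she might be accompanied.
- On an intervention day, a support person who is uneasy about the procedure room has a reason to decline, and the patient is then lost as well.

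Both primary aims in section 1.1.2, pain on the VAS and state anxiety on the STAI, are self-reported. Both plausibly vary with how much a patient wants support and with her tie to the support person. Those are the traits that could decide enrolment, so the arms could differ before treatment, and a larger sample would not remove the difference.

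**Working it through.** **Order of events.** Putting sections 1.3.1, 1.3.6, 1.3.8 and 1.3.8.1 in sequence:

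1. The slip is drawn at the start of the day. The envelope hides it only up to that moment.
2. The patient consents to the procedure.
3. Research staff approach the patient, then the support person.
4. The research assistant confirms eligibility, and the pair consent to the study.
5. The demographic form, expected-pain VAS and STAI are completed.
6. The patient goes to the procedure, accompanied or not.

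The arm is fixed at step 1 and is not needed until step 6. No section says at which step it is disclosed, and none withholds it between steps 1 and 4. Section 4.1 prints the demographic form in two versions headed by arm, so as written whoever hands it out at step 5 needs to know the arm.

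**What the forms capture.** The demographic form (section 4.1) asks the relation between patient and support person. The post-procedure forms (section 4.2, item 8; section 4.3, item 4) ask whether the patient would choose to be accompanied. The relation item does not measure strength of preference. The preference item comes after treatment and may be changed by it. Neither exists for pairs who decline. Expected pain and STAI are taken before the procedure, but section 1.3.12 itself anticipates that control patients' anxiety may already be raised at that point.

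**Illustration of size.** The plan gives no figure on this point to reproduce. From section 1.3.2 I take the SD of 23 mm and 100 patients per arm (reading 200 participants per arm as 100 patients and 100 support persons). Everything else is assumed:

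- *p*, the share of eligible patients who strongly want company: 0.5
- *d*, the share of these who decline on control days: 0.2 to 0.5 (none decline on intervention days)
- *D*, the gap in the analysed pain outcome between them and other patients: 10 to 20 mm

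Share of strong-preference patients among control enrolees = p(1 − d) / [p(1 − d) + (1 − p)].
Bias in the arm difference = (p − that share) × D.

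| d | Control share | Bias, D = 10 mm | Bias, D = 20 mm |
|---|---|---|---|
| 0.2 | 0.40/0.90 = 0.444 | 0.56 mm | 1.11 mm |
| 0.4 | 0.30/0.80 = 0.375 | 1.25 mm | 2.50 mm |
| 0.5 | 0.25/0.75 = 0.333 | 1.67 mm | 3.33 mm |

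Standard error = 23 × √(2/100) = 3.25 mm, ignoring clustering by day.

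A wider grid (p 0.3 to 0.5, d 0.2 to 0.6, D 5 to 20 mm) gives a bias b of 0.2 to 4.3 mm. The chance that a two-sided 5% test rejects a true null is 1 − Φ(1.96 − b/SE) + Φ(−1.96 − b/SE), which runs from 5.1% to 26% over that grid. The direction depends on who declines. If those who want company report more pain, losing them from the control arm lowers the control mean and hides a benefit; if they report less, the reverse. Refusals by support persons on intervention days would add a shift of unknown direction. No figure is given for anxiety, because the protocol states no SD for the STAI.

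**The case against.** The strongest case against runs as follows.

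- **Disclosure is not documented.** A reader might infer that pairs know their arm when they decide, and so that the arms will differ. The documents do not support that. The statement in section 1.3.1 that patients cannot be kept from knowing their arm explains why patients are not randomised individually; it does not say when they learn it. The wording in section 1.3.12, that control patients may not have their support person, fits uncertainty as well as knowledge. This stands: the bias is possible, not shown.
- **Roles.** Section 1.3.6 gives the approach to research staff generally and requires all patients to be approached, which limits recruiter choice. This stands in part. The research assistant still starts enrolment and confirms eligibility, and approaching everyone does not govern who accepts.
- **One entry rule.** Section 1.3.4 applies the same criteria to both arms, and section 1.3.2 defines support persons as chosen to accompany the patient. True, but nothing asks a control support person whether they would go in, and what taking part involves differs by arm.
- **Weak incentive.** Section 2 says support persons are seldom allowed in, section 1.6 names provider support as a main worry, and decliners lose a $10 gift card. This stands as a reason to expect modest refusal, and the refusal rates above have no source in the protocol.
- **Measured traits.** A reader might infer that no planned form touches the relevant traits. That is wrong, given the relation and preference items. They still do not supply a pre-treatment measure of preference or any data on decliners.
- **Size.** The largest tabulated bias is one sixth of the 20 mm taken as clinically significant (3.33/20), and it needs a gap between patient types as large as that 20 mm. This stands for a large pain effect, but not for smaller effects.

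**Conclusion.** The concern holds as a risk. The arm is set before recruitment by a role that also enrols, it is not concealed from recruiter or pair, and entry depends on willingness that can respond to it. Randomising days therefore does not secure the comparability that section 1.3.12 expects, although that sentence is already hedged and is not shown to be false. Analysis could not reliably correct such selection with the forms planned. The illustrative bias, about 0.6 to 3.3 mm against a standard error of about 3.3 mm, rests wholly on assumed refusal rates and pain gaps and ignores clustering by day. It shows that the problem could be as large as the sampling error, not that it will be. Concealment lost at enrolment cannot be restored afterwards, so the protocol text is the place to deal with it.

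**What to change.** - **Sections 1.3.1 and 1.3.8:** keep the day's slip sealed, held where possible by existing staff who do not recruit. Disclose the arm to the pair, and as far as practicable to the recruiter, only after both have consented and the pre-procedure VAS, STAI and demographic forms are complete. Use one demographic form without an arm in its heading; the two versions in section 4.1 ask the same items.
- **Section 1.3.8:** before disclosure, have every support person in both arms confirm that they would be willing to enter the procedure room.
- **Enrolment log (section 1.3.10):** record every eligible pair approached, with refusals and reasons by day, and report participation by arm.
- **Section 1.3.12:** qualify the sentence on similar groups to acknowledge possible differential enrolment.

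The cost is protocol wording, a sealed slip and extra entries in a log that already exists. Section 1.3.8.1 already places consent and the pre-procedure forms ahead of the procedure, so the visit order need not change. Later disclosure would also shield baseline anxiety and expected pain from knowledge of the arm. The limit is that later pairs on the same day may guess the arm, and anyone tracking the ten-slip block can work out its last day, so concealment would be better but not complete.

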1.6 Problems Anticipated

One of the greatest concerns regarding this study is provider support. Providers at the Tampa Health Center will be required to permit support persons in the room.

Other potential problems include the potential frustration on the part of patients who may desire to have support person in the room but are not permitted to do so.

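### Procedure days are allocated by hand from a fixed, repeating block of ten slips written in the protocol, so the next day's arm can often be guessed and the draw leaves no record

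*Protocol*

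**What the plan says.** The unit of randomisation is the clinic day: "Each procedure day will be randomized into" an accompanied or an unaccompanied day (Protocol 1.3.1). On the mechanics, "Randomization will occur at the beginning of each procedure day by a research assistant", who is to "pull from an opaque envelope that contains ten slips of paper, five will be marked with 'A' and the other five marked with 'B". A means intervention and B means control. The slips stay out until the block is used up: "After all ten slips of paper are pulled and ten of the procedure days have been randomized", the assistant "will replace the ten slips of paper and begin the same randomization process until the designated number of participants have been enrolled". The same section gives the research assistant role the job of starting enrolment.

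Two other sections bear on this. Section 1.3.12 concedes that "One potential weakness is that blinding cannot occur". Section 1.6 says that "One of the greatest concerns regarding this study is provider support", and adds that providers must allow support persons in and that some patients may be frustrated at being refused one.

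The protocol mentions no sequence generated in advance, no varying or undisclosed block size, no individually sealed or numbered assignments, and no witness or log for the draw.

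**The concern.** The block is always ten days, its make-up is written down, draws are without replacement, and past arms are visible to everyone in the clinic. A count of past days therefore gives the remaining slips, and the arm of a coming day can be guessed better than by chance, sometimes with certainty. If patients' appointments or providers' turns were arranged with that knowledge, the arms could differ in patient mix or provider for reasons other than chance. Because a whole day is the unit, one steered day moves all of that day's patients. Section 1.3.12 relies on randomisation to make the groups alike, and pain and anxiety are self-reported in an unblinded setting.

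The second weakness is that the draw cannot be verified. One on-site person takes a loose, unnumbered slip from an envelope that must stay accessible for ten procedure days. If a slip were put back and another drawn, nothing described in the protocol would show it.

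This is not the same as the day's arm being known when that day's patients are approached. Enrolling patients before the draw would address that, but would leave future days guessable and the draw without a record.

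**Working it through.** **Inputs.** Block of ten days with five A and five B, drawn without replacement and repeated (Protocol 1.3.1); past arms known (1.3.12). The plan gives no predictability figure of its own to reproduce. Lead time between booking and the procedure day, and the total number of days, are not in the protocol and are assumptions where used.

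**1. Guessing the next day when all earlier draws are known.** After i draws, of which a were A, the probability of that state is C(5,a)·C(5,i−a)/C(10,i). Naming the arm with more slips left is right with probability max(5−a, 5−i+a)/(10−i). A day is certain when one letter is used up. Over all C(10,5) = 252 sequences:

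| Day in block | 1 | 2 | 3 | 4 | 5 | 6 | 7 | 8 | 9 | 10 |
|---|---|---|---|---|---|---|---|---|---|---|
| Guess correct, % | 50 | 55.6 | 55.6 | 59.5 | 59.5 | 64.3 | 64.3 | 72.2 | 72.2 | 100 |
| Day certain, % | 0 | 0 | 0 | 0 | 0 | 0.8 | 4.8 | 16.7 | 44.4 | 100 |

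- Expected correct guesses: 823/126 = 6.53 of 10, or 65.3%. The closed form agrees: 5 + (2^10/252 − 1)/2 = 5 + (4.063 − 1)/2 = 6.53.
- Expected certain days: 2n/(n+1) with n = 5, so 10/6 = 1.67 of 10, or 16.7%.
- At least two days are certain in 44.4% of blocks.
- The guess is right with probability 2/3 or more on 38.7% of days.

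**2. Effect of lead time.** If a decision is made while k earlier procedure days are still undrawn, the undrawn slips are exchangeable. The chance of a correct guess is then the table value k days earlier, and 50% for the first k days of a block. The table rows sum to 653.2 (correct) and 166.7 (certain).

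- k = 1: correct (653.2 − 100 + 50)/10 = 60.3%; certain (166.7 − 100)/10 = 6.7%.
- k = 2: correct (653.2 − 100 − 72.2 + 100)/10 = 58.1%; certain (166.7 − 100 − 44.4)/10 = 2.2% (unrounded inputs).

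**3. What an alternative would give.** Under a big-stick design each day is a fair coin toss, except that the lagging arm is forced once the A−B difference reaches a limit. The guess rate is 50% plus half the share of forced days. For 26 and 40 days (assumed):

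| Scheme | Correct guesses | Days forced | Mean absolute A−B difference at end |
|---|---|---|---|
| Present block of ten | 65.3% | 16.7% | about 1.1 days (stopped at 26 days) |
| Big-stick, limit 3 | about 57.5–57.8% | about 15% | about 1.3 days |
| Big-stick, limit 4 | about 55% | about 10% | about 2.0 days |

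Random blocks of 6, 8 or 10 give 65.5–65.9% correct guesses. Undisclosed sizes remove certainty but do not lower the average guess rate.

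**The case against.** The strongest reply is that predictability does harm only if someone can act on it, and the protocol shows no route for that. It does not describe booking, rebooking or rostering. Patients are approached only after they have presented and consented to the procedure (1.3.1, 1.3.6). Providers are required to admit support persons (1.6), and 1.3.12 describes a small rotating group working to common standards. The 65.3% and 1.67 days apply only to someone deciding after the previous day's slip is known, and the advantage shrinks quickly with lead time. All of this stands, and it is why no size of bias can be given.

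Three stronger readings are tempting and should be resisted.

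- *That draws are being repeated.* Nothing says so. The envelope is described as opaque, 1.3.10 gives the principal investigator and research manager the task of monitoring adherence to the protocol, and a site procedure could exist elsewhere. A redraw could also only reorder days, since each completed block must hold five A and five B.
- *That steering could never be seen or adjusted for.* Sections 1.3.8.1 and 4.1 collect gestational age, previous abortions, sedation, expected pain and STAI before the procedure, and 1.3.11 compares characteristics between arms. Some shift in patient mix would show. Expected pain and STAI are less clean for this purpose, because 1.3.12 accepts that knowing the arm may raise baseline anxiety. Unmeasured differences could still be missed.
- *That the guess rate converts into a bias in millimetres of VAS.* That needs the difference between patients or providers on days predicted as A and as B, which the protocol does not give. The comparison between arms is also of change in VAS (1.3.11), so part of any difference in level would cancel.

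It is also fair to say that drawing the day's arm before that day's patients are approached is the more direct concealment weakness. It remains whatever is done here.

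**Conclusion.** The point holds as a weakness in a rule that the protocol itself fixes, not as a missing detail. With all earlier draws known, the next day's arm can be guessed on 65.3% of days against 50%, with 1.67 of ten days certain on average and the tenth always so. With one earlier day undrawn the figures are 60.3% correct and 6.7% certain; with two, 58.1% and 2.2%. They rest on the stated block and on past arms being known to staff. Whether anyone could use the information is not documented, so the bias is of unknown size and may be nil.

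The missing record of the draw is a vulnerability. A reader might infer that allocation was manipulated, or that the results could not be trusted; the protocol supports neither. The change is worth making because it is cheap and is best made before enrolment.

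**What to change.** Rewrite the allocation paragraph of Protocol 1.3.1 along these lines:

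- The existing study statistician, who should have no part in recruitment, generates the day sequence in advance by a less predictable method. One example is big-stick with limit 4.
- The limit, or any block sizes, are withheld from clinic staff and kept out of the protocol. This matters: if limit 4 became known, about 10% of days would be recognisable as forced, and about 15% with limit 3. Undisclosed random block sizes are a weaker fallback, for the reason given in the check.
- The sequence is held in sealed, opaque, consecutively numbered envelopes or on a central list. One assignment is released per procedure day, after that day's appointment list and provider are recorded. Each opening is logged and the envelopes are kept.
- The sentence on replacing the ten slips is deleted.

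The cost is one amended paragraph and a set of envelopes or a short list, with no extra patients or staff. The downside is slightly unequal numbers of days per arm: a mean absolute difference of about 2 days with limit 4, against about 1.1 for the present scheme stopped at 26 days.

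This change does not deal with the day's arm being drawn before that day's patients are approached, which needs its own remedy.
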